3.0 Protocol Synopsis

Study Summary	
Study Purpose	The aim of this study is to evaluate the potential improvement in colonoscopy procedure's outcomes when using the Pure-Vu System in hospitalized subjects who are indicated for colonoscopy procedure.
Objective	The primary objective of this study is to evaluate the bowel cleansing after Pure-Vu use in hospitalized subjects, which may increase the likelihood of a successful colonoscopy examination.
Study procedures	
❖ Eligible subjects will be consented and enrolled❖ Following standard bowel preparation, the nurse or study coordinator will be asked to complete a questionnaire about the subjects' baseline preparation condition prior to the colonoscopy procedure.❖ Subjects will undergo colonoscopy procedure with Pure-Vu System.❖ In case of inadequate bowel preparation as defined as BBPS < 2 in at least one of the colon segments, prior Pure-Vu use, the physician will complete a questionnaire on the patient's management standard of care assuming the absence of Pure-Vu.
Protocol Number	CL00044
Protocol Title	Evaluation of the bowel cleansing in hospitalized population using Pure-Vu System Ver. 4.0

Document Title: Evaluation of the bowel cleansing in hospitalized population using Pure-Vu System	Document No. CL00044	Version 4.0	Page 8 of 44
---	--------------------------------	-----------------------	--------------

Study Sponsor	Motus GI Medical Technologies, [name] [contact] [contact]
Sponsor Representative	[name] VP Health Economics, Regulatory and Clinical Affairs
Study Type	Multicenter, prospective, feasibility study
Study Product	Pure-Vu System
Study Phase	Post-market
510 (k) Number	K181437 Class II
Study Location	United States and Europe
Study Duration	Study period will last approx. 12 months
Planned Follow-Up	Follow-up will be conducted at 2 working days post-procedure to assess subject well-being and capture any adverse events.
Subject Population	Hospitalized subjects who are indicated for standard colonoscopy procedure and meet the eligibility criteria.
Determination of Sample Size	This is a pilot study that will include up to 100 subjects; no statistical considerations were made to determine the sample size.
Planned # of Sites	Up to 6 clinical sites
Primary Endpoint	The rate of improved cleansing level per segment will be evaluated by the Boston Bowel Preparation Score (BBPS) index.

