10.0 Study Design

[figure not shown]
This multicenter, prospective, single arm study will include up to 100 subjects (up to 35 subjects per site), aimed at evaluating the performance of the Pure-Vu System in cleansing hospitalized subjects' colon who are indicated for standard colonoscopy procedure. Subjects will be enrolled at up to 6 clinical sites in the United States and Europe

- ❖ Subject consent will be obtained
- ❖ Prior to the colonoscopy procedure, the nurse or study coordinator will be asked to complete a questionnaire including the subjects' bowel preparation type, volume, duration and overall preparation condition.
- ❖ The subject will undergo the colonoscopy procedure with the Pure-Vu system.
- ❖ In case of inadequate bowel preparation defined as BBPS score less than 2 in at least one of the colon segments prior Pure-Vu use, the physician will complete a questionnaire on the patient's management standard of care assuming the absence of Pure-Vu.

Document Title:	Document No.	Version	Page 21 of 44
Evaluation of the bowel cleansing in hospitalized population using Pure-Vu System			

- ❖ Following the colonoscopy with Pure-Vu a follow-up evaluation will be conducted at 48 hours (\pm 48 hours) to assess subject's well-being and capture any adverse events. If the subject is no longer hospitalized, the follow up will be conducted by a telephone call.

Study Flowchart

Document Title:	Document No.	Version	Page 22 of 44
Evaluation of the bowel cleansing in hospitalized population using Pure-Vu System	CL00044	4.0	

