The colonoscopy examination with the Pure-Vu will be recorded on digital media. Only the subject study ID and initials should appear in the recorded video.

The cecum will be documented in a picture, if applicable.

Document Title:	Document No.	Version	Page 27 of 44
Evaluation of the bowel cleansing in hospitalized population using Pure-Vu System	CL00044	4.0	

All optical colonoscopy still pictures will be saved in a digital format. Quality copies of the pictures taken during optical colonoscopy will be provided to the sponsor and the optical colonoscopy report will be reviewed as part of the monitoring process.

These videos and pictures will be archived and may be used in future analyses to, for example, provide further information about observed lesions or to assess study quality.

Specific situations occurring during colonoscopy

- If the attempt to reach the cecum is failed, the investigator shall perform the procedure with a pediatric or any other colonoscope he/she may choose without Pure-Vu. The subject will complete the study as planned.
- If a medical condition requiring treatment is detected during colonoscopy, the subject will be treated as per the standard care.

Post-Examination Follow-up

Subjects will be transferred to recovery room for observation per clinical site's colonoscopy protocol and will continue his/her medical flow as per the standard of care. Follow-up will be conducted 2 business days (+/- 48 hours) after the procedure to verify that there has been no change in their well-being. Any AE will be documented in the CRF.

Before a subject is considered "lost to follow-up", there must be at least two documented attempts to contact the subject.

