14.1 Adverse Event (AE)

An AE is any untoward medical occurrence, unintended disease or injury, or untoward clinical signs (including abnormal laboratory findings) in subjects, whether or not related to the investigational medical device.

This definition includes events related to the investigational medical device or the comparator and the procedures involved.

AEs will be collected starting from the time subject is enrolled until the follow-up period is completed.

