14.10 Adverse Event Recording and Reporting

Assessment of the occurrence of an AE will be based on changes in the subject's signs and symptoms. AEs will be monitored until a subject completes the study unless the Investigator determines the event is related to the investigational device, in which case they will be monitored until resolution if possible. Medical care will be provided, as defined in the informed consent, for any AE related to study participation. AEs will be collected on an AE CRF and applicable source documentation.

The following should not be considered an AE:

- A condition requiring a preplanned procedure unless the condition worsened since screening
- A preexisting condition found as a result of screening, unless the condition has worsened since enrollment.

All AEs observed during the course of this study, regardless of severity or relationship to the investigational device will be recorded on the appropriate CRF.

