20.0 Appendixes A: Study Design and Schedule of Assessment

	Visit 1	Follow Up
Days	0	2 Business Days (± 48 hours)
Informed Consent	X	
Eligibility assessment (medical records, BMI, etc.)	X	
Medical History, Concomitant Medications, and Demographic details	X	
Assessment of patient's bowel preparation questionnaire	X	
*Assessment of patient's management Directions (filled-in by the physician)	X	
Colonoscopy Procedure	X	
Follow Up	X	X
Adverse Events Reporting	X	X

*for subjects with inadequate bowel cleansing level in at least one segment at baseline.

Document Title:	Document No.	Version	Page 44 of 44
Evaluation of the bowel cleansing in hospitalized population using Pure-Vu System			

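### The post-procedure follow-up window is stated inconsistently and can reach down to hour 0, so adverse-event observation time is neither fixed nor equal across subjects

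*Combined protocol and SAP*

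**What the plan says.** Four places in the protocol time the follow-up contact:

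- Synopsis, Planned Follow-Up: "Follow-up will be conducted at 2 working days post-procedure". No tolerance is given.
- Section 10.0: "a follow-up evaluation will be conducted at 48 hours", with a tolerance of plus or minus 48 hours. The contact is by telephone if the subject has left hospital.
- Section 12.5, Post-Examination Follow-up: "Follow-up will be conducted 2 business days (+/- 48 hours) after the procedure".
- Appendix A, Follow Up column: "2 Business Days (± 48 hours".

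Section 14.1 sets the collection period: "AEs will be collected starting from the time subject is enrolled until the follow-up period is completed". Section 14.10 adds: "AEs will be monitored until a subject completes the study unless the Investigator determines the event is related to the investigational device". In that exception, monitoring goes on to resolution where possible.

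AE type, incidence, severity and duration form a secondary endpoint (section 9.2). Section 13.4.1 provides listings and summarises AEs as counts and percentages, with no allowance for observation time. Section 11.0 puts participation at roughly 3 days, counting the procedure day and follow-up. No section states a minimum post-procedure observation time.

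**The concern.** A tolerance as long as the target interval removes the lower limit: 48 h minus 48 h is 0 h. A very early contact can then satisfy the protocol. If that contact is taken to complete follow-up, it also closes AE collection for that subject.

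The wordings also give different windows for the same subject, so a site cannot tell which one governs and a monitor cannot classify deviations consistently.

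What is at stake is the safety result. Section 7.1 names perforation, pain, infection and bleeding as risks. Events that begin after collection closes are not counted, and compared with a common longer window a shorter one can only lose events. Duration is affected as well. Events not judged device-related are monitored only to study completion, and section 14.8 codes an event still present then as continuing, so an early end cuts the recorded duration short.

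**Working it through.** The plan states no figure to reproduce on this point. The check is window arithmetic, followed by a labelled illustration.

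**Step 1: windows.** Inputs are the target and tolerance from section 10.0 (48 h, 48 h) and from section 12.5 and Appendix A (2 business days, 48 h). The window is target minus tolerance to target plus tolerance. Assumptions: business days are Monday to Friday, there are no holidays, and days are counted whole.

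| Procedure day | Section 10.0 window | Target, 12.5 / Appendix A | Window, 12.5 / Appendix A |
|---|---|---|---|
| Mon, Tue, Wed | 48 ± 48 = 0–96 h | 48 h | 0–96 h |
| Thu, Fri | 0–96 h | 96 h (weekend skipped) | 96 ± 48 = 48–144 h |
| Sat | 0–96 h | 72 h | 72 ± 48 = 24–120 h |
| Sun | 0–96 h | 48 h | 0–96 h |

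The lower edge is hour 0 for every subject under section 10.0. Under section 12.5 and Appendix A it is hour 0 for Sunday to Wednesday procedures only.

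**Step 2: conflicts.** Take a Thursday procedure.

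- A contact at 24 h lies inside 0–96 h (section 10.0) and outside 48–144 h (section 12.5).
- A contact at 120 h lies outside the first window and inside the second.
- Only 48–96 h satisfies both.

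The synopsis target matches section 12.5 and Appendix A. With no tolerance, though, it read literally makes any contact off the target day a deviation.

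**Step 3: spread of observation time.** Across the two wordings, compliant contacts run from 0 to 144 h after the procedure. All subjects enter one crude percentage.

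**Step 4: illustration only.** The documents give no distribution of AE onset. Assume exponential onset with median m hours. The share of post-procedure AEs that have begun by a contact at t hours is 1 − 0.5^(t/m).

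| Contact at | m = 12 h | m = 24 h | m = 48 h | m = 72 h |
|---|---|---|---|---|
| 0 h | 0% | 0% | 0% | 0% |
| 24 h | 75% | 50% | 29% | 21% |
| 48 h | 94% | 75% | 50% | 37% |
| 96 h | 99.6% | 94% | 75% | 60% |

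With an assumed true incidence of 10% and m = 24 h, the expected recorded rate is 10% × share: 0%, 5.0%, 7.5% and 9.4% for contacts at 0, 24, 48 and 96 h. These figures show that the recorded rate depends on contact time. They do not estimate the bias in this trial.

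**The case against.** The case for leaving the plan alone has substance, and several stronger readings that a reader might infer do not hold.

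- *This is the only safety contact.* It is not. Appendix A marks follow-up and AE reporting at Visit 1 as well, and section 12.5 has recovery-room observation. It is the only scheduled contact after the procedure day.
- *Hour 0 is allowed for everyone under every wording.* It is not. Under section 12.5 and Appendix A the earliest compliant contact is 48 h for Thursday and Friday procedures.
- *A recovery-room check certainly ends AE collection.* Section 14.1 refers to the follow-up period, not to the contact, so this is a possible reading and not a stated rule. Section 12.5 describes recovery separately from follow-up, and the stated participation of about 3 days shows that a later contact was intended.
- *Sites will tend to make early contact because subjects are still inpatients.* No section gives length of stay or discharge timing, and section 10.0 provides for subjects already discharged.
- *The AE rate is biased by a known amount.* No onset data are given, so no amount can be derived.

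It is also fair that this is a single-arm pilot with a descriptive safety summary and no safety threshold, and that the primary endpoint is untouched.

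These points narrow the concern without removing it. An approximate participation length sets no minimum, and no section removes the zero lower edge. Following device-related events to resolution helps only for events already identified, not for later onset. Routine ward care may notice later events, but the protocol does not say that they are collected once follow-up is complete.

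**Conclusion.** The point holds in limited form. The timing statements conflict, and a contact at or near hour 0 can comply: for all subjects under section 10.0, and for Sunday to Wednesday procedures under section 12.5 and Appendix A. Compliant contacts span 0 to 144 h across the wordings, with no analysis that accounts for the difference. AE incidence and duration, a secondary endpoint, may therefore be understated.

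The window arithmetic rests only on the documents and a Monday-to-Friday business week. The effect on the AE rate further depends on reading the contact as the end of the follow-up period, on when sites actually make contact, and on AE onset times. The documents settle none of these, so the direction can be argued but the size cannot be computed. This is a wording defect worth correcting because the correction is cheap. It does not invalidate the trial.

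**What to change.** - Reconcile the synopsis, section 10.0, section 12.5 and Appendix A into one window, in clock hours from the end of the procedure, with a lower limit above zero. The sponsor sets the hours.
- State in section 14.1 that AE collection stays open until a contact inside that window, and that an earlier contact is repeated.
- In section 13.4.1, report the post-procedure observation time beside the AE rate, for example hours per subject and the share contacted inside the window.

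The cost is protocol wording, a few repeat calls or bedside checks, and possibly a slightly higher reported AE rate.

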13.0 Statistical Analysis

13.1 Sample Size Determination

This is a pilot study that will include up to 100 subjects; no statistical considerations were made to determine the sample size.

Document Title: Evaluation of the bowel cleansing in hospitalized population using Pure-Vu System	Document No. CL00044	Version 4.0	Page 28 of 44
---	--------------------------------	-----------------------	---------------

13.2 Description of statistical methods

Basic demographic and other baseline characteristics will be collected and analyzed for all subjects. Summary statistics (mean, standard deviation, median, minimum and maximum for quantitative variables) will be presented for the total study population. Frequency tables for qualitative data will be provided.

Any deviation from specified statistical plan will be in addition to “per protocol” analysis and will be reported as such. Intent-To-Treat and Post-hoc analysis will be conducted according to the existing data gathered, if necessary.

13.3 Primary Endpoint Analysis

The primary endpoint is improving the bowel cleansing level, as determined by BBPS scoring index, assessed per segment (cecum and ascending / transverse / descending, sigmoid and rectum).

The primary statistical hypothesis is that the cleansing level post Pure-Vu procedure will be significantly improved as compared to the cleansing level pre procedure (prior the Pure-Vu use). The primary performance assessment will be based on data from all colon segments observed during the colonoscopy procedure.

The count and percentage of segments and subjects with improved BBPS after the Pure-Vu cleansing procedure will be presented together with 95% confidence intervals.

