6.3 Clinical data to Date

The Pure-Vu System was evaluated in ninety-seven subjects (54% males) from five sites using similar protocol.

Pure-Vu was used in subjects indicated for a screening, diagnostic or surveillance colonoscopy. To ensure an inadequately prepped colon, subjects underwent a reduced preparation consisting of dietary restrictions (no dried fruit, seeds or nuts) starting 2 days prior to the colonoscopy, an 18 to 24 hour clear liquid diet and a split dose of 20mg Bisacodyl.

The cleansing quality was evaluated before and after use of the Pure-Vu System with the Boston Bowel Preparation Score (BBPS) (1).

Two subjects were excluded from the analysis due to the followings: One subject had breakfast on day of procedure and therefore was excluded from the cleansing efficacy and usability analysis due to non-compliance with the pre-procedural prep regimen. The other subject was excluded because the device could not reach beyond the sigmoid colon due to the subject's

Document Title: Evaluation of the bowel cleansing in hospitalized population using Pure-Vu System	Document No. CL00044	Version 4.0	Page 17 of 44
---	--------------------------------	-----------------------	---------------

anatomy, thus the physician used a slim colonoscope to complete the procedure and indicated that only a slim colonoscope would be able to advance past the sigmoid and into the cecum.

The Pure-Vu significantly increased the number of subjects with an adequate cleansing level (BBPS ≥ 2 for all 3 colon segments) from 25%; CI 95% [17%, 35%] at baseline to 99%; CI 95% [94%, 100%] after Pure-Vu. Cecum intubation rate was 98%; CI 95% [94%, 100%]). Mean post-treatment BBPS score was 8.7 ± 1.0 vs. 3.9 ± 2.2 prior to Pure-Vu use. Physicians were satisfied with the device's use. No major difficulties were experienced when performing polypectomy and no serious adverse events were reported.

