9.0 Study Endpoints

9.1 Primary endpoints

The rate of improved cleansing level per segment will be evaluated by the BBPS (1) scoring index pre- and post- Pure-Vu use during a colonoscopy examination.

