13.4.2 Efficacy Analysis

Cecal Intubation Rate

The count and percentage of subjects for which cecum could be reached by the colonoscope with the Pure-Vu will be presented together with 95% confidence intervals.

Proportion of subjects with successful colonoscopy at first attempt

Successful colonoscopy at first attempt is defined as complete procedure conducted as scheduled for the intended indication.

Frequency counts, percentages, and 95% confidence intervals will be provided. In addition, the above proportion will be compared vs. the proportion of subjects that would have underwent a complete procedure at first attempt assuming absence of the Pure-Vu System (as per the data to be captured by the Patient Management Direction). Chi-square or Fisher's exact test, as appropriate, will be performed to evaluate the difference between the two clinical set-ups.

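### Section 13.3 states a hypothesis of significant pre-to-post improvement, but the planned percentage improved with 95% CIs does not test it, leaves subject-level improvement undefined and ignores clustering of segments

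*Combined protocol and SAP*

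**What the plan says.** Section 9.1 sets a per-segment endpoint: "The rate of improved cleansing level per segment will be evaluated by the BBPS" index before and after use. Section 13.3 adds a hypothesis, "The primary statistical hypothesis is that the cleansing level post Pure-Vu procedure will be significantly improved as compared to the cleansing level pre procedure", and the unit of assessment: "The primary performance assessment will be based on data from all colon segments observed during the colonoscopy procedure". The analysis itself is one sentence: "The count and percentage of segments and subjects with improved BBPS after the Pure-Vu cleansing procedure will be presented together with 95% confidence intervals".

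Section 13.3 gives no test, significance level, null value or success criterion. It does not ask for unchanged or worsened counts, define improvement for a subject, or name a method for the intervals. Section 13.2 adds only summary statistics and frequency tables. The one inferential procedure named in section 13 is in 13.4.2, where a chi-square or Fisher's "exact test, as appropriate, will be performed to evaluate the difference between the two clinical set-ups". That concerns first-attempt success, a secondary endpoint. Section 13.1 says: "This is a pilot study that will include up to 100 subjects; no statistical considerations were made to determine the sample size".

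**The concern.** A claim of significant improvement over baseline is a paired comparison: gains must be weighed against losses within the same subjects. The percentage improved describes only the gains. A confidence interval can stand in for a test when there is a null value to compare it with. Here there is none, and the natural one (improved and worsened equally likely) depends on a count that the plan does not ask for.

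Two gaps in the same section add to this. A subject contributes up to three segments, and a subject could count as improved if any segment, every segment or the average score rises. Preparation quality is also likely to be similar across one subject's segments, so the segments are not independent observations.

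At stake is whether a later statement that cleansing was significantly improved would have a prespecified basis. As written, the test and the subject-level definition would have to be chosen after the data are seen.

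**Working it through.** The plan states no power, significance level or derived sample size, so it has no design figure to reproduce. As a check on the interval method, the earlier study in section 6.3 can be reproduced. With 97 − 2 = 95 subjects analysed, exact (Clopper-Pearson) intervals give 24/95 = 25% (17 to 35) and 94/95 = 99% (94 to 100), matching the reported figures.

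**Inputs.** Up to 100 subjects (13.1) and three segments each (13.3), so up to 300 segments. Two-sided 0.05 is assumed, to match the 95% intervals. Improved and worsened counts and the intraclass correlation (ICC) are assumptions, because the documents give none.

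**1. Does the planned output test the hypothesis?** Take 30 of 100 subjects improved. The exact 95% interval is 21.2% to 40.0%, whatever happened to the other 70. The exact two-sided sign test compares improved (I) with worsened (W) and drops ties: p = min{1, 2 × P(X ≥ I)}, with X ~ Binomial(I + W, 0.5).

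| Improved | Worsened | Planned interval | Sign-test p |
|---|---|---|---|
| 30 | 0 | 21.2–40.0% | 2e-9 |
| 30 | 15 | 21.2–40.0% | 0.036 |
| 30 | 16 | 21.2–40.0% | 0.054 |
| 30 | 30 | 21.2–40.0% | 1.0 |

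The planned output is the same in every row and the answer to the hypothesis is not.

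**2. Does the subject-level definition matter?** Assume that each segment improves with probability 0.5, under a beta-binomial model for three segments with a = b = 0.5(1 − ICC)/ICC. Then P(no segment improves) = [a/(2a)] × [(a+1)/(2a+1)] × [(a+2)/(2a+2)], and by symmetry P(all improve) is the same.

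- ICC 0.3: 0.5 × 0.65 × 0.731 = 0.238. Any segment improved: 76% of subjects. All segments improved: 24%.
- ICC 0.7: 0.5 × 0.85 × 0.912 = 0.388. Any segment improved: 61%. All segments improved: 39%.

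The same segment data can therefore give very different subject rates.

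**3. What does ignoring clustering do?** With three segments per subject, the design effect is 1 + 2 × ICC. That is 1.6 at ICC 0.3 and 2.4 at ICC 0.7, so the effective number of segments is 300/1.6 = 187.5 or 300/2.4 = 125. For an assumed 90/300 segments improved (30%):

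- treated as independent: 24.9% to 35.5%, width 10.7 points;
- ICC 0.3: 23.5% to 37.1%, width 13.6 points, ratio 1.27;
- ICC 0.7: 22.1% to 38.8%, width 16.7 points, ratio 1.57.

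**4. How would an effect like the earlier study's fare?** Subjects with adequate cleansing rose from 24 to 94 of 95. Only one was inadequate afterwards, so either 70 gained and 0 lost adequacy, or 71 gained and 1 lost it. The sign test on either split gives p far below 0.001.

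**The case against.** The strongest reply is that the gap hardly matters in practice. Worsening during irrigation and evacuation is unlikely: on the figures in section 6.3, at most 1 of 95 subjects lost adequacy. With 0, 1, 2 or 5 subjects worsened, a sign test is already significant at 6, 8, 10 or 15 improved. The rows above with 15 or more worsened show what the output cannot distinguish; they are not a forecast. This stands, and it limits the severity.

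The earlier study does not carry over directly, because "To ensure an inadequately prepped colon, subjects underwent a reduced preparation", whereas here section 12.4 follows standard practice and section 11.1 does not require a poorly prepared bowel. More segments could start clean and have little room to improve. But section 12.4 also does not require the preparation to be completed, and section 5.1 names inpatient status as a risk factor for failed preparation. The documents do not settle the direction.

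Section 13.2 says that departures from the plan will be additional and labelled as such. That helps transparency, but it does not supply a test for the stated hypothesis. Pilot status excuses the lack of a power calculation, not a significance hypothesis without a test.

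A reader might infer a sharper rule: that the planned output settles the hypothesis only if the subject-level lower limit exceeds 50%. The documents contain no such threshold. It is a worst-case bound that needs a sign test, an exact interval and a net-score definition of subject improvement. Under those conditions, 61/100 (50.7% to 70.6%) passes even if the other 39 worsened (p = 0.035), and 60/100 (49.7% to 69.7%) does not (p = 0.057). Change a condition and it fails:

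- A Wilson interval already exceeds 50% at 60/100 (50.2% to 69.1%).
- With 61 subjects at +1 and 39 at −3, the mean change is (61 − 117)/100 = −0.56, and the signed-rank test gives p = 0.024 in the direction of worsening.

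**Conclusion.** The point holds in a limited form, as a minor one. Section 13.3 states a significance hypothesis that its planned analysis does not test, and nothing else in section 13 fills the gap. This follows from the text and needs no assumption; the example of one interval with p-values from 2e-9 to 1.0 rests on assumed counts. The undefined subject-level outcome is likewise plain from the text. The understatement of segment-level interval width, by a factor of about 1.3 to 1.6, assumes ordinary binomial intervals, three scored segments per subject and an ICC of 0.3 to 0.7.

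It would be wrong to infer that the study is likely to miss a real effect. The earlier study reports that the device "significantly increased the number of subjects with an adequate cleansing level", and an effect of similar size would probably be clear under any reasonable paired test. What is missing is the prespecified link between the hypothesis and an analysis.

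**What to change.** Amend section 13.3 in two respects.

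1. Choose one of two routes.
   - *Test the hypothesis.* Name one two-sided 0.05 paired test at subject level, for example a Wilcoxon signed-rank test on each subject's change in mean BBPS over segments scored both before and after. Define a subject as improved if that mean rises. Report the numbers improved, unchanged and worsened.
   - *Or describe only.* Remove the significance hypothesis and call the primary analysis descriptive, which suits a pilot with no statistical basis for its size. Subject-level improvement still needs the same definition if its percentage is reported.
2. On either route, use cluster-robust or subject-level bootstrap confidence intervals for the segment rates.

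No new data are needed, and the per-segment endpoint in 9.1 is unchanged. The cost is a wording amendment with the sponsor and IRB approvals that section 15.2 requires, a little more analysis, and wider segment intervals than a binomial calculation would show. The descriptive route also gives up a formal significance claim.
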